3.0 Study Data Collection

3.1 *Study Data Collection Intervals*

Refer to Section 5, Study Procedures and Evaluations, in the study protocol (MD151471).

3.2 *Study Interval Windows*

Subjects with successful study device implant will return for follow-up visits at 30 days, and at 6, 12, and 36 months. For the 24-month assessment, subjects will be contacted by telephone. Subjects considered Technical Failures (study device attempted but not implanted) are only required to complete a 30-day follow-up telephone assessment and will then be discontinued from the study. All intervals are calculated from the index procedure (day 0). The visit windows are calculated as the target day plus or minus the appropriate number of calendar days. The 6-month visit target is 180 days. The yearly visits are calculated on a 365-day year from index procedure.

30 Days	6 Months	12 Months (1 Year)	24 Months (2 Years)	36 Months (3 Years)
30 ± 14 days	180 ± 14 days	365 ± 60 days	730 ± 60 days	1095 ± 60 days

³ Hintze, J. (2013). PASS 12. NCSS, LLC. Kaysville, Utah, USA. www.ncss.com

3.3 *Independent Data Review Board (IDRB)*

Excerpt from section 9.7 of the study protocol:

During the course of the study, the IDRB will serve as both a Data and Safety Monitoring Board (DSMB) and Clinical Events Committee (CEC). As the DSMB, the IDRB will review aggregate safety data for the course of the study to monitor the incidence of SAEs and other safety trends that could warrant modification or termination of the study. As the CEC, the IDRB will adjudicate all site-reported adverse events through 30 days post-procedure for seriousness and relatedness of potential primary endpoint events. In addition, the IDRB will review and adjudicate all site-reported AEs related to arrhythmia for the course of the study. The IDRB Charter will outline the responsibilities and operating procedures of the Board.

3.4 *Site Enrollment Restrictions*

A maximum of 22⁴ investigative sites in the United States will participate in this study. One hundred twenty-five (125) non-training subjects will be enrolled in the Pivotal Phase of this study, with a limit of 10 non-training subjects enrolled at any single site during the Pivotal Phase. The first 2 subjects enrolled at each site will be considered training cases that do not apply to the above restrictions.

If approval is obtained to resume enrollment in the Continued Access Phase, up to 335 additional subjects may be enrolled. No individual site enrollment restrictions will apply to the Continued Access Phase.

3.5 *Core Lab*

All protocol-required echocardiographic and fluoroscopic imaging will be uploaded to the study imaging vendor's secure web portal. The core lab will access images via the secure web portal and perform evaluations on the 30-day, 6-, 12-, and 36-month echocardiographic images. Results of core lab evaluations will be recorded in the study database.

4.0 Statistical Analyses and Methods

4.1 *Analysis Sets*

The co-primary endpoints will be analyzed under several different analysis set definitions, as described below.

4.1.1 *Primary Analysis Set*

There is no single primary analysis set for this clinical investigation, because the two co-primary endpoints each require different analysis sets, as described below.

⁴ Although the current version of the study protocol (MD151471 Revision 2) states a maximum of 30 participating sites, approval for 22 sites was granted by FDA in IDE Supplement G160218/S001 dated January 3, 2017.

CONFIDENTIAL INFORMATION

MD133254 Statistical Analysis Plan Template

Revision#: 1

Doc Type: GC

9 of 13

4.1.2 All Enrolled Subjects Analysis Set

This analysis set is defined as all subjects with a study device implant attempt, regardless of whether the study device was successfully implanted. The 6-month clinical success co-primary endpoint will be analyzed using this set, as will technical success, procedure success, and 30-day safety. However, because technical failures (study device attempted but not implanted) are followed only to 30 days, this set will not be used for the analysis of the 6-month closure success co-primary endpoint, nor any other postprocedure measures or outcomes.

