Subject Population	

• No age limitations

• Patients with ostium secundum ASD measuring 8-35 mm by stop-balloon sizing

• Inter-atrial shunting with evidence of right heart volume overload, demonstrating the need for septal defect closure

• Absence of concurrent cardiac conditions that could elevate morbidity/mortality beyond what is common for ASD

Number of Subjects	

• Training Cases: First 2 subjects per site

• Pivotal Phase: 125 subjects (non-training)

• Continued Access Phase: up to 535 subjects (non-training)

• Total Study Enrollment: up to 704 subjects

Number of Sites	Up to 22 sites in the U.S.
Coordination Principal Investigator	
[REDACTED]
 
[REDACTED]
 
[REDACTED]
 
National Principal Investigator, Pediatric
 
[REDACTED]
 
[REDACTED]
 
[REDACTED]
 
National Principal Investigator, Adult

Significant Inclusion Criteria	

• Patient has an ostium secundum ASD with evidence of left-to-right shunt and right ventricular volume overload.

• Patient has a defect size 8-35 mm as measured directly by stop-flow balloon sizing.

• Patient vasculature can accommodate the delivery system and procedural accessories.

• Patient can accommodate TEE or intracardiac echocardiography (ICE) probe for implant procedure.

• Patient is judged by the implanting physician to have adequate septal rims to retain the study device.

 
[REDACTED]
 
[REDACTED]

	

• [REDACTED]

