2.2 Design Summary

The Gore ASSURED Clinical Study is a prospective, multicenter, single-arm clinical study comparing outcomes for the GORE® CARDIOFORM ASD Occluder to performance goals derived from clinical investigation outcomes for devices indicated for ASD closure.

This clinical investigation will enroll up to 460 subjects (not including 2 training cases per site) from a protocol-specified maximum of 22¹ clinical investigational sites (referred to as “sites” in the remainder of this document) in the United States. Enrollment will occur in three phases: Pivotal (125 subjects, in addition to 2 training cases per site); Continued Access (up to 335 subjects); and Post-Approval (if required). Each phase will enroll sequentially.

All enrolled subjects with technical success will be followed through the 36-month follow-up; subjects with technical failure will be followed only through the 30-day follow-up. The analysis in support of pre-market approval submission will occur when the 125 pivotal (non-training) subjects have completed 6-month follow-up evaluations.

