2.3 Randomization and Enrollment

This is a single-arm clinical study with no concurrently enrolled control subjects for comparison, and thus randomization is not applicable.

A patient is considered an enrolled subject in the study when the test device enters the patient’s vasculature, also referred to as “test device attempted.” Enrollment of the subject is indicated in the study data system by a response of Yes to Question 1 of the ENRL (Enrollment) CRF, *Was the study device introduced into the anatomy of the subject?*

¹ Although the current version of the study protocol (MD151471 Revision 2) states a maximum of 30 participating sites, approval for 22 sites was granted by FDA in IDE Supplement G160218/S001 dated January 3, 2017.

CONFIDENTIAL INFORMATION

MD133254 Statistical Analysis Plan Template

Revision# 1

Doc Type: GC

3 of 13

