4.1.3 Technical Success Analysis Set

This analysis set is defined as all subjects with a successful study device implant, (i.e. technical success). The 6-month closure success co-primary endpoint will be analyzed using this set, as will all other postprocedure measures or outcomes except technical success, procedure success, and all assessments of clinical success.

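### Do the co-primary analysis sets in SAP 4.1.2 and 4.1.3 wrongly admit training cases and Continued Access subjects?

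*SAP*

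**What the plan says.** SAP 4.1.2 (All Enrolled Subjects Analysis Set) gives the population for the Composite Clinical Success test, technical success, procedure success and 30-day safety: "This analysis set is defined as all subjects with a study device implant attempt, regardless of whether the study device was successfully implanted". SAP 4.1.3 (Technical Success Analysis Set) gives the population for the 6-Month Closure Success test: "This analysis set is defined as all subjects with a successful study device implant". Neither definition mentions phase or training status.

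Enrolment is defined in SAP 2.3 by device entry: "A patient is considered an enrolled subject in the study when the test device enters" the vasculature. Training cases meet that definition, and SAP 3.4 describes them as enrolled: "The first 2 subjects enrolled at each site will be considered training cases that do not apply to the above restrictions". The restrictions meant there are the Pivotal enrolment of 125 and the limit of 10 non-training subjects per site.

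On when and on whom the primary analysis is done, SAP 2.2 says: "The analysis in support of pre-market approval submission will occur when the 125 pivotal (non-training) subjects have completed 6-month follow-up evaluations". SAP 4.2.1 ties the primary endpoint analysis to completed 6-month follow-up of the Pivotal Phase cohort. The protocol's Study Summary lists training cases, the Pivotal Phase (125, marked non-training) and Continued Access on three separate lines.

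**The concern.** In a single-arm trial tested against a fixed performance goal, the analysis set fixes the denominator, and the denominator fixes the number of successes needed. A set defined only by attempted or successful implant takes in every such subject in the study. The first two patients at each site would then count towards a confirmatory test, although the design treats them as learning cases. Continued Access subjects could count as well. The term Pivotal Phase cohort in 4.2.1 and 4.2.2 has no formal definition, and one phrase in 2.2 describes the Pivotal Phase as 125 subjects in addition to two training cases per site. That leaves some room to argue over which side of the line training cases fall.

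At stake would be an undeclared choice of denominator that could be made after the results are known. A related worry is 30-day safety: 4.1.2 assigns it to all attempted subjects, while 4.2.2 bases the interim submission on the Pivotal Phase cohort, so training-case events might not appear in that submission.

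**Working it through.** **1. Enrolment figures.** Inputs: the protocol Study Summary (22 sites, 2 training cases per site, 125 Pivotal, up to 535 Continued Access, total 704) and SAP 2.2 (125 Pivotal, up to 335 Continued Access, total 460 without training cases).

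- SAP: 125 + 335 = 460, as stated.
- Protocol: 125 + 535 + 2 × 22 = 704, as stated: "Total Study Enrollment: up to 704 subjects". Training cases are counted in this total.

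The two Continued Access sizes differ because the SAP cites protocol Revision 2 and the supplied protocol is Revision 6. That is a separate matter.

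**2. How many training cases could enter.**

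- Maximum: 2 × 22 = 44, giving 125 + 44 = 169, of which 44/169 = 26% are training cases.
- Minimum if all 125 are enrolled under the cap of 10 per site: 125/10 rounds up to 13 sites, so 26 training cases and 26/151 = 17%.

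**3. Effect on the pass mark.** SAP 4.3.1 specifies an exact binomial test at one-sided 5%. The pass mark is the smallest r with P(X ≥ r | n, goal) ≤ 0.05. The goals are redacted, so three values are assumed. The denominators shown are for Composite Clinical Success; those for 6-Month Closure Success count technical successes only and may be smaller.

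| Assumed goal | n = 125 | n = 169 | Difference in rate |
|---|---|---|---|
| 0.80 | 108 (86.4%), p = 0.042 | 145 (85.8%), p = 0.033 | 0.6 points |
| 0.85 | 114 (91.2%), p = 0.029 | 152 (89.9%), p = 0.040 | 1.3 points |
| 0.90 | 119 (95.2%), p = 0.028 | 159 (94.1%), p = 0.043 | 1.1 points |

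So the choice of set would matter if it were truly open.

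**4. Could Continued Access subjects be in the primary analysis?** SAP 4.2.2 lets Continued Access begin only after 30-day follow-up is complete on all Pivotal subjects and approval has been obtained. Count days from the last Pivotal procedure. By target days, the last Pivotal 6-month visit is day 180, and the earliest Continued Access 6-month visit is 30 + 180 = day 210. At the extremes of the SAP 3.2 windows (±14 days for both visits), the earliest Continued Access visit is (30 − 14) + (180 − 14) = day 182, against 180 + 14 = day 194 for the last Pivotal visit. Any overlap would need the interim analysis, submission and approval to take less than 194 − 182 = 12 days in total. All-phase denominators (460 + 44 = 504 on SAP figures, 704 on protocol figures) are therefore not realistic for the confirmatory tests.

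**5. Is the choice open?** Set the sections side by side:

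- SAP 4.1.2 and 4.1.3 classify by treatment status: attempted or implanted.
- SAP 4.2.1, under Timing of Analyses, gives the phase for the primary endpoint analysis: Pivotal.
- SAP 2.2 names the subjects behind the pre-market submission: the 125, expressly non-training.
- SAP 3.4 says the Pivotal Phase enrols 125 non-training subjects and exempts training cases from those limits.
- The protocol summary labels the Pivotal 125 as non-training and lists training cases on their own line.

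Treatment status and phase are two separate dimensions. Combined, they give one population per test: the Pivotal non-training subjects with an attempt for Composite Clinical Success, and those among them with technical success for 6-Month Closure Success.

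**The case for a change.** The best argument for a change is that SAP 4.1 is where analysis sets are defined, and its visible words do not limit phase or training status. The statements in 2.2 and 4.2.1 are mainly about timing, so the exclusion of training cases is inferred and nowhere stated outright. The consequence can also run either way. At an assumed goal of 0.85, 114/125 passes, but adding 37/44 training successes gives 151/169, one short of the 152 needed. Conversely 113/125 fails, but adding 39/44 gives 152/169, which passes. A choice able to reverse a result is better fixed in writing, and one clause would do it.

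What stands is that 4.1.2 and 4.1.3 are silent, that no visible sentence expressly bars training cases from the tests, and that the arithmetic is right. What does not stand is that the plan contradicts itself or leaves two equally supported readings. Each section that names the Pivotal number with a training qualifier says non-training, and even the looser phrase in 2.2 keeps the training cases on top of the 125. Phase-neutral sets also have a plausible use, since the same SAP serves Continued Access and 36-month reporting. The reversal examples rest on assumed goals and outcomes; nothing visible shows how training cases would perform or in which direction a bias would run.

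The safety point is weaker. The 4.2.2 submission involves no formal testing. SAP 3.3 has the Independent Data Review Board review aggregate safety data throughout and adjudicate every site-reported event through 30 days, with no exception for training cases. A separate training-case column would be a preference in presentation.

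**Conclusion.** No change to the plan is needed. SAP 4.1.2 and 4.1.3 leave a detail unstated, and the protocol summary and SAP 2.2, 3.4 and 4.2.1 supply it: the co-primary tests belong to the 125 non-training Pivotal subjects, restricted to technical successes for 6-Month Closure Success. An analyst following the whole plan would use that population and reach a sound conclusion, so an added clause would only write down what is already indicated.

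Had the choice been open, the most that training cases could do is raise the denominator from 125 to 169 and lower the required success rate by 0.6 to 1.3 percentage points at the three assumed goals of 0.80, 0.85 and 0.90. Continued Access inclusion at the primary analysis is practically ruled out by the sequence of approvals and visits.

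Two limits apply. The performance goals are redacted, so the pass marks are illustrative. SAP 2.6 and 2.7 are redacted and only the protocol summary is available, so an explicit restriction may already exist there; its absence is shown only for the visible text.

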2.5 Study Endpoints

2.5.1 Primary Endpoints

Co-Primary Endpoint 1: 6-Month Closure Success is defined as a clinical residual defect status of occluded or clinically insignificant as determined by the Echo Core Lab at the 6-month evaluation among subjects with technical success.

Co-Primary Endpoint 2: Composite Clinical Success is evaluated at 6 months after index procedure among subjects with attempted study device closure and is defined as satisfying all of the following criteria:

1. Technical Success: Successful deployment and retention (at conclusion of index procedure) of a GORE® CARDIOFORM ASD Occluder
2. Safety Success:
 - Freedom from any Serious Adverse Event (SAE) related to the device or procedure, as adjudicated by the Independent Data Review Board (IDRB) through 30 days post-procedure
 - Freedom from device events (post-procedure embolization, device removal, or other device reintervention) from completion of the implant procedure through 6 months (180 days) post-procedure
3. Closure Success: A clinical residual defect status of occluded or clinically insignificant as determined by the Echo Core Lab at the 6-month evaluation.

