2.5.2 Secondary Endpoints

Technical Success: Successful deployment and retention of the study device at the conclusion of the index procedure

Procedure Success: Technical success and measured residual defect status of occluded, small, or moderate of the target ASD at conclusion of the index procedure

Long-term Closure Success: Closure success evaluated at 12 months and 36 months

Long-term Composite Clinical Success: Composite clinical success evaluated at 12 months and 36 months

CONFIDENTIAL INFORMATION

MD133254 Statistical Analysis Plan Template

[figure not shown]
[figure not shown]
[figure not shown]
Revision#: 1

Doc Type: GC

Safety Outcomes: The proportion of subjects experiencing one or more SAEs within 30 days post-index procedure, and the proportion of subjects experiencing a device event (embolization; device removal; reintervention after completion of index procedure) through 6 months, 12 months, and 36 months post-index procedure

Clinically Significant New Arrhythmia: In subjects without prior history of arrhythmia, any new arrhythmia (documented on ECG) requiring hospitalization, initiation of new long-term medical therapy (persisting > 45 days), or any post-index procedure cardioversion or intervention (pacemaker, ablation, etc.)

2.6 *Statistical Hypotheses*

CONFIDENTIAL INFORMATION

MD133254 Statistical Analysis Plan Template

Revision# 1

Doc Type: GC

2.7 *Sample Size Determination*

2.7.1 [REDACTED]

CONFIDENTIAL INFORMATION

[figure not shown]
MD133254 Statistical Analysis Plan Template

Revision#: 1

Doc Type: GC

A series of six horizontal black bars of varying lengths, each ending in a small white bracket on the right side. The bars are arranged vertically, with the longest bar at the top and the shortest at the bottom. The brackets are positioned at the end of each bar, pointing to the right.

2.7.2

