4.4 Secondary Endpoints

Secondary endpoints (subject-based unless otherwise specified) will be descriptive only; no formal statistical hypotheses will be tested. Secondary endpoints will be summarized at the specified time points using the descriptive statistics described above. No claims of statistical significance will be made based on secondary endpoint results. Any p-values from these tests will not be reported in labeling, but may be used for scientific presentations and manuscripts.

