4.9.2 Sensitivity Analyses

Sensitivity analyses of the clinical closure and clinical success co-primary endpoints will be conducted and will include, at a minimum, a "worst-case" analysis (subjects who withdraw or are lost to follow-up are considered failures), a "best-case" analysis (subjects who withdraw or are lost to follow-up are considered successes), and, if necessary, a tipping point analysis (threshold of imputed successes vs. failures at which the primary test conclusion changes).

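### Does Long-term Composite Clinical Success at 12 and 36 months have no analysis set it may be reported on?

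*SAP*

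**What the plan says.** The endpoint is named in SAP 2.5.2: "Long-term Composite Clinical Success: Composite clinical success evaluated at 12 months and 36 months". It takes over the composite defined in SAP 2.5.1, where "Composite Clinical Success is evaluated at 6 months after index procedure among subjects with attempted study device closure"; the first of the three criteria there is technical success.

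The analysis sets are in SAP 4.1:

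- **4.1.2, All Enrolled.** Used for the 6-month clinical success co-primary endpoint, technical success, procedure success and 30-day safety. The section then states that "this set will not be used for the analysis of the 6-month closure success co-primary endpoint, nor any other postprocedure measures or outcomes". The reason it gives is that follow-up of technical failures ends at day 30.
- **4.1.3, Technical Success.** Used for 6-month closure success and the other postprocedure outcomes, "except technical success, procedure success, and all assessments of clinical success".
- **4.1.4, Per-Protocol.** A restriction of either set above, for additional analyses if they are needed.

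On follow-up, SAP 3.2 says that technical failures "are only required to complete a 30-day follow-up telephone assessment and will then be discontinued from the study". On inference, SAP 4.4 makes the secondary endpoints "descriptive only; no formal statistical hypotheses will be tested".

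**The concern.** The 12- and 36-month composite is not on the 4.1.2 list, so the closing bar in that section appears to catch it. The exception in 4.1.3 removes it from the other main set, and 4.1.4 offers only optional subsets of the same two. A named endpoint then seems to have no main analysis set.

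The denominator matters for this endpoint. If a programmer took the 4.1.2 bar at face value and reported the long-term composite on implanted subjects, every subject in the table would meet the technical success criterion by construction. The rate would be too high, and it could not be compared with the 6-month composite, which is reported on all attempted subjects.

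**Working it through.** The plan states no figure for this endpoint, so there is nothing to reproduce. The check is a comparison of sections, followed by the size of the error if the wrong set were used.

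**Which set the sections point to**

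1. *Population in the definition.* SAP 2.5.1 attaches the composite to subjects with an attempted device. SAP 2.3 makes that the definition of enrolment, and 4.1.2 makes it the definition of All Enrolled. SAP 2.5.2 changes the time point and nothing else.
2. *Exclusion from the alternative.* The exception in 4.1.3 covers every assessment of clinical success. The plan has three: 6, 12 and 36 months. If only the 6-month one were meant, a universal exception would have no purpose.
3. *Reason for the bar.* 4.1.2 bars All Enrolled because technical failures leave the study after 30 days. That matters for outcomes that need a device in place or later visits, such as those for which the core lab will "perform evaluations on the 30-day, 6-, 12-, and 36-month echocardiographic images". It does not matter for the composite: a technical failure fails criterion 1 on day 0, and no later visit can alter that.
4. *The plan's own precedent.* The 6-month composite also lies beyond 30 days, yet 4.1.2 assigns it to All Enrolled. The sponsor therefore already treats technical failures as classifiable for this composite without later follow-up. The same holds at 12 and 36 months.

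All four lines lead to All Enrolled, with technical failures counted as failures.

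**Size of the error if the Technical Success set were used, against 4.1.3**

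Let p be long-term success among implanted subjects and f the technical failure rate. The documents give neither, so both are assumed.

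- Rate on All Enrolled = p × (1 − f)
- Rate on Technical Success = p
- Overstatement = p × f

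Low end: 0.80 × 0.02 = 1.6 points. High end: 0.95 × 0.08 = 7.6 points.

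In counts, take the 125 pivotal subjects (SAP 2.2 and 3.4) and an assumed success of about 90% among implanted subjects:

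| Technical failures (assumed) | Successes | All Enrolled | Technical Success | Gap, points |
|---|---|---|---|---|
| 0 | 112 | 112/125 = 89.6% | 112/125 = 89.6% | 0.0 |
| 2 | 111 | 111/125 = 88.8% | 111/123 = 90.2% | 1.4 |
| 5 | 108 | 108/125 = 86.4% | 108/120 = 90.0% | 3.6 |
| 10 | 104 | 104/125 = 83.2% | 104/115 = 90.4% | 7.2 |

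These gaps measure a choice that the plan prohibits. On the set the plan points to, the gap is zero.

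**The case for a change.** The strongest case for a change is that intent should not have to be inferred against the words. As written, 4.1.2 forbids the set that everyone would use. 4.1.3 lists clinical success as an exception to postprocedure outcomes, which suggests that the plan counts it among them and that the bar in 4.1.2 therefore reaches it. The output specifications required by SAP 6.0 could record the right set, but they are not among the documents and would depart from the letter of 4.1.2. The repair would cost a few words.

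Part of this stands: the list in 4.1.2 is incomplete and its last clause is too broad. The argument from the exception list is weak, though. The same list includes technical success and procedure success, both judged at the end of the index procedure, so appearing there does not make an outcome postprocedure. The repair would also change no result; it would only write down what the other sections already settle.

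A second argument concerns implanted subjects whose 12- or 36-month outcome is missing. SAP 4.9.2 says "Sensitivity analyses of the clinical closure and clinical success co-primary endpoints will be conducted", and no visible section extends these analyses to the long-term composite. With assumed counts of 125 attempted, 10 technical failures, 35 implanted subjects lost and 72 successes among the 80 evaluable, the rate is 72/125 = 57.6% if the lost count as failures and (72 + 35)/125 = 85.6% if they count as successes. The arithmetic is right, but it describes assumed attrition and has nothing to do with the analysis set. An evaluable-only rate, 72/(80 + 10) = 80.0%, rests on a denominator that no section prescribes. It also treats technical failures as the only subjects whose failure is known early, whereas a related serious adverse event by day 30 or an early device event settles failure before any later loss. Limiting the formal sensitivity analyses to the co-primary endpoints is a reasonable choice when the secondary endpoints carry no test.

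**Conclusion.** No change to the plan is called for. The wording of 4.1.2 leaves a gap that analysts will fill sensibly: the definition in 2.5.1, its reuse in 2.5.2 and the exclusion in 4.1.3 leave All Enrolled as the only workable set, and the stated reason for the bar does not apply to subjects who have already failed the composite.

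The effect on results is nil if that set is used. The 1.6 to 7.6 points arise only from using the set that 4.1.3 excludes, and they rest on assumed values of p (80% to 95%) and f (2% to 8%). Both co-primary endpoints have explicit sets, the pre-market analysis is made at 6 months (SAP 4.2.1), and the test hierarchy in 4.3.2 does not involve this endpoint. This conclusion assumes that the analysts read 4.1.2 together with 2.5.1 and 4.1.3. The table specifications under SAP 6.0 are a natural place to name the denominator.
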